9.1.2 Secondary Objectives/Outcomes

The models proposed will be tested using general linear models (GLM). We will examine all variables to determine that they are relatively symmetric and unimodal, examine group variances for obvious deviations, and examine the residuals from each model to ensure reasonable adherence to the assumptions of normality and independence. If any variables violate the assumptions, we might transform skewed variables. We will evaluate the comparability of our groups on key demographic variables and will covary variables if necessary (e.g., socioeconomic status). For Efficacy Outcome Measure 1 (refer to section 1.2.1), we will use repeated measures ANOVA or ANCOVA (including intracranial volume as a covariate for macrostructure analyses) with Group (Treatment, Control) as the between-subjects factor and Time of Assessment (baseline, 1 year, and 2 years) and Age as the within-subjects factors. We

will examine the Age x Group x Time interaction and two-way interactions for each analysis and will trim non-significant terms from each model. If GM and WM volumes or DTI metrics vary across time, we will complete trend analysis to identify whether a linear or quadratic function best fits the data. Dependent variables will be evaluated in separate analyses. Dependent variables will be 1) the volume of whole brain gray matter, white matter, and CSF; 2) FA of core white matter pathways (corpus callosum, arcuate/superior longitudinal fasciculus), and 3) MD of gray matter in frontal and temporal cortical regions.

To examine brain-behavior relations (Efficacy Outcome Measure 2, section 1.2.2), we will first examine the distribution of variables to determine whether assumptions are met for Pearson or Spearman correlation approaches. To evaluate strength of brain-behavior relations, outcome scores will be correlated with specific macrostructural and microstructural metrics from the DTI. For global outcome, the GOS-EC score will be correlated with gray and white matter volumes and corpus callosum FA. For neurocognitive outcomes, the accompanying table shows the expected relations between outcomes and gray and white matter microstructural metrics. We expect positive correlation of dependent variables with FA and negative correlation of dependent variables with MD. Similar to our recent approach ([name] et al., 2012), brain-behavior analysis will also be completed using individual outcomes as dependent variables with group (Treatment, Control) and MRI/DTI variables as independent variables (e.g., examine the effect of group and FA of the corticospinal tract on fine motor scores; examine group and MD of dorsolateral frontal cortex on working memory scores).

Expected Relations of Neurocognitive Outcomes with Gray and White Matter						
Microstructure from Diffusion Tensor Imaging.						
Neurocognitive	Microstructure:	Microstructure:				
Outcome	Gray Matter MD	White Matter FA				
IQ		Corpus callosum				
Motor		Corticospinal				
GMFM-88						
Verbal Fluency		Arcuate/superior longitudinal				
PPVT4/EVT2		fasciculus				
Learning/Memory	Temporal cortex,					
NEPSY-II	hippocampus					

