6.4.8 MRI Quality Control Procedures

At the time of acquisition, we have procedures to check the aMRI and DTI data for outliers and confounding artifacts due to acquisition (e.g. image geometric distortions, field in homogeneity, signal-to-noise-ratio) and motion. If problems occur during scan acquisition, the sequence will be repeated to optimize image quality within the same imaging session based on real-time evaluation of imaging data and decisions made by [name]. All post-processing procedures of aMRI and DTI data include highly interactive protocols (i.e., not fully automated) requiring visual inspection of the data at each processing stage, which provides the best assurance of image quality. A standard water phantom will document and monitor scan quality at each imaging session. Post-processing procedures include quantitative evaluation of eddy currents and head movement using ExploreDTI v4.8.1 software provided by [name]. Evaluation of DTI data acquired from our living phantom in Houston is presented below in Figures 11 and 12. Our criteria for disqualifying DTI datasets and re-acquiring DTI data within the

same imaging session are translations greater than one voxel (e.g. 2 mm) or rotations greater than 1°.

Figure 11

Figures 11: Quantitative evaluation of DTI data quality using Explore DTI v 4.8.1. On the left, the percentage of outlier voxels is plotted as a function of diffusion-weighted gradient direction number and slice number. On the right, rotations, translations, scale, and skew are plotted for each cardinal plane as a function of diffusion-weighted direction number.

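### The imaging analysis drops, by default, any child missing one of three scans and picks demographic covariates by observed imbalance; a mixed model with fixed covariates is a modest, cheap improvement

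*Combined protocol and SAP*

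**What the plan says.** Section 9.1.2 names the general linear model as the framework and, for Efficacy Outcome Measure 1, states "we will use repeated measures ANOVA or ANCOVA". Group (Treatment, Control) is the between-subjects factor, with "Time of Assessment (baseline, 1 year, and 2 years) and Age as the within-subjects factors". One covariate is fixed in advance: "including intracranial volume as a covariate for macrostructure analyses". For demographic variables, the groups are first compared and the team "will covary variables if necessary"; socioeconomic status is the only example, and there is no list or threshold. After fitting, the team "will trim non-significant terms from each model".

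No section gives an imputation rule, a mixed model, a missing-data method or an expected loss rate for this analysis. Section 9.1.1 mentions repeated-measures modelling for the safety data without detail. Section 8.4 asks a child who withdraws for an exit evaluation with the content of the 12-month visit, which under Appendix A includes DT-MRI. Section 8.5 rules out replacement. Section 3 sets 30 children randomised 2:1 and offers sham children cells at 12 months.

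**The concern.** Repeated-measures ANOVA fitted as a general linear model normally uses only children with every repeated value. The plan does not spell out listwise deletion, but the named method does this by default and nothing in the plan overrides it. The protocol's own procedures can produce incomplete series: a child who withdraws and attends the exit evaluation has a baseline and an exit scan but no 2-year scan, and both scans would be discarded.

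The missing value that costs most is the one that helps least. Once sham children have crossed over, the 2-year scan no longer compares cells with sham, yet its absence removes a 1-year scan that does.

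Choosing demographic covariates by observed imbalance makes the model depend on the data and gives up precision from variables that could be fixed now. Cell source is absent from the pooled model although the two sources are recruited and randomised separately (Sections 5.1 and 5.2). GMFCS level, which spans II to V at entry (Section 4.1), is absent too. Age is listed as within-subjects, although age at entry varies between children.

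At stake is the precision of a comparison with about 10 sham children, whose imaging data are meant to inform the powering of later studies (Section 6.4.9).

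**Working it through.** **The plan's own figure.** Section 3 ties 30 children to a 15% volume effect but gives no SD, power or dropout rate. It cannot be reproduced as a power calculation and does not bear on this point.

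**Inputs.** From the plan: 30 children at 2:1, so 20 treated and 10 sham; scans at baseline, 1 year and 2 years; significance level 0.05 (taken as two-sided). Assumed: loss rate m per scan, independent between visits and equal in both groups; within-child correlation r.

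**Step 1: children contributing at 1 year, loss at follow-up only.** Complete cases = 30(1 − m)². Children with a 1-year scan = 30(1 − m). The SE ratio, ignoring the little that is borrowed from other visits, is √(complete cases ÷ children with a 1-year scan) = √(1 − m).

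| m | All three scans | 1-year scan | SE reduction |
|---|---|---|---|
| 5% | 27.1 | 28.5 | 2.5% |
| 10% | 24.3 | 27.0 | 5.1% |
| 20% | 19.2 | 24.0 | 10.6% |

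**Step 2: detectable effect.** Noncentral t, 80% power, two-sided 0.05:
- 20 v 10, nothing missing: 1.12 SD
- 18 v 9, children with a 1-year scan at m = 10%: 1.19 SD
- 16 v 8, complete cases at m = 10%: 1.27 SD

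The choice of method accounts for the step from 1.27 to 1.19. The step from 1.19 to 1.12 is data that no method recovers.

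**Step 3: baseline scans also lost at rate m.** Complete cases = 30(1 − m)³, which is 21.9 at 10%. Generalised least squares on all observed scans was compared with complete cases for the baseline-to-1-year group contrast, with r from 0.7 to 0.95 and the covariance treated as known. The SE fell by 4–5%, 8–9% and 17–18% at m = 5%, 10% and 20%.

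**Step 4: baseline adjustment.** Baseline is already a level of Time, so the planned Group × Time contrast is a change-score comparison with relative SE √(2(1 − r)). Adjusting for baseline gives √(1 − r²).
- r = 0.7: √0.6 = 0.775 against √0.51 = 0.714, a reduction of about 8%
- r = 0.9: √0.2 = 0.447 against √0.19 = 0.436, a reduction of about 2.5%

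**Step 5: covariate chosen by imbalance.** 20,000 simulated null trials, 20 v 10, one covariate. The plan gives no threshold, so two were assumed: imbalance p < 0.05, and a group difference above 0.25 SD.

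| Rule | r = 0.5: type I error, SD of estimate | r = 0.7: type I error, SD of estimate |
|---|---|---|
| Always adjust | 0.051, 0.342 | 0.053, 0.285 |
| Adjust if p < 0.05 | 0.043, 0.376 | 0.037, 0.364 |
| Adjust if difference > 0.25 SD | 0.040, 0.346 | 0.033, 0.292 |

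Here r is the covariate–outcome correlation. Against the p < 0.05 rule, always adjusting cuts the SD of the estimate by 1 − 0.342/0.376 = 9% and 1 − 0.285/0.364 = 22%. Against the looser rule the cuts are about 1% and 2%. Both selective rules are conservative.

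**The case against.** The strongest reply is that this is a secondary analysis in a trial described as primarily a safety study, that the gain is small, and that the plan already deals with part of the problem. Much of that stands.

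- **DTI quality control.** A reader might take "Our criteria for disqualifying DTI datasets" in Section 6.4.8 as evidence that children will be lost. Read in full, the sentence covers re-acquisition in the same session, so it mainly prevents missing data. It also applies only to DTI; the volumes come from the T1 series (Section 6.4.4).
- **Withdrawals.** Section 8.4 does seek an exit evaluation. That limits loss of 1-year information but leaves the series one scan short, so the named analysis still drops the child.
- **Covariates.** It would be wrong to say that every covariate depends on imbalance. Intracranial volume and Age are specified; the selection rule concerns demographic variables. Nor does the simulation show false positives. The cost is precision, and its size depends on an unstated threshold.
- **Size.** One might quote 1.12 against 1.27 SD, or a 29% SE cut from a covariate correlated 0.7 (1 − √0.51). The first compares with no missing data at all. The second compares with no adjustment, although baseline is already in the model.
- **Bias.** The blind is broken before the 1-year visit, so attendance could come to differ by assignment. No section shows that it will, and differential loss remains conjecture.

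What survives is that a method is named, it discards usable scans by default, and a better one needs no further data.

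**Conclusion.** The point holds as an improvement of modest size that should be made. With 10% of scans lost at each follow-up, about 27 rather than 24 children contribute at 1 year, the detectable effect is about 1.19 rather than 1.27 SD, and the SE is about 5% lower (8–9% if baseline scans are lost at the same rate). Baseline adjustment instead of change adds about 2.5% to 8%. All of this rests on assumed loss rates and correlations, because the documents give none; at 5% loss the first gain falls to 2.5%.

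A reader might infer that the efficacy comparison is biased or that its error rate is inflated. The documents support neither. A mixed model is itself valid only if scans are missing at random, and it does not repair the crossover; reading the contrast at 1 year does that.

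**What to change.** Amend Section 9.1.2 as follows:

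- Fit a linear mixed model by REML to all observed scans, with separate group means at each follow-up visit and a small-sample degrees-of-freedom correction such as Kenward–Roger. State the missing-at-random assumption.
- Use baseline either as an outcome visit with group means constrained equal, or as a covariate, but not both. The first option keeps a child whose baseline scan is missing.
- Fix a short covariate list now: cell source, age at entry as a between-child covariate, GMFCS as one ordinal or dichotomised term, and intracranial volume for the volume outcomes. Keep these terms whether or not they are significant, and delete selection by observed imbalance.
- Read the randomised contrast at the 1-year scan before any crossover infusion. Section 5.2.7 allows the cord blood infusion just before or just after the scan, and Section 5.2.10 applies the same procedures at crossover, so state how a 1-year scan taken after infusion will be handled.

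The cost is revised wording, slightly more programming and three or four degrees of freedom for covariates. With about 10 sham children the list should stay that short. No extra children, scans or visits are needed.

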1.2 Secondary Objective

To determine if late functional outcomes are improved following the administration of autologous cells compared with subjects in the control group. Efficacy outcome measures:

- 1. aMRI volumetric white matter, grey matter, and CSF space volumes at Baseline, 1 year and 2 years post-treatment. Detailed volumetric analysis of the corpus callosum and white matter tract such as the corticospinal tract will be measured (fractional anisotropy and mean diffusivity) as well. Specific white matter tract analysis will be identified at baseline MRI and correlated with motor function studies as the primary lesion of interest. Total volumes and specific tract lesions will be analyzed and correlated with functional outcomes.
- 2. The following functional outcomes studies will be performed at baseline, 6 months, 1 year after infusion, and 2 year after infusion.
 - a. Gross Motor Function Measures
 - b. Psychological Assessment Batteries

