3. STUDY DESIGN

This is a randomized, blinded, placebo-controlled, cross-over study designed to treat CP in pediatric subjects with an IV infusion of autologous bone marrow mononuclear cells or autologous umbilical cord blood cells. A total of 30 subjects (15/arm) will be enrolled into the study. Subjects will be randomized 2:1 (treatment: sham). All subjects will return for follow-up at 6 months, 12 months, and 24 months post-treatment. At the 12 months post-treatment visit, those subjects who originally received the sham will be offered the BMMNC or hUCB treatment (Figure 1).

Figure 1.

Thirty subjects will provide a preliminary assessment of potential SAEs with a 10 to 15% incidence that we would be able to detect with reasonable confidence. The sample size would also allow us to acquire point estimates of different events that we would use for a larger efficacy study. The sample size determination is based on the historical treatment effect size of 15% decrease in gray and white matter volumes. Preservation

of this volume is based on the Phase 1 pediatric acute treatment of severe TBI using autologous bone marrow derived mononuclear cells as compared to historical control volumetric analyses by Wilde et al. (Wilde, E, et. al. 2005; Cox, C et al., 2011.)

Drug/Biologic: A single dose of intravenously administered autologous BMMNC or hUCB. The BMMNC dose will be 6X10⁶ cells/kg body weight infused over 15 minutes at a 1 million cells/ml concentration. For the hUCB arm, the minimum acceptable dose will be 2X10⁶cells/kg body weight based on rodent data (Lu, 2001), and the maximum allowable dose will be 10X10⁶cells/kg. The target dose will be the maximum available dose within this range. The bone marrow harvest, the hUCB reanimation, cell processing and product infusion will occur at Children's Memorial Hermann Hospital and the Griffin Stem Cell Laboratory.

Placebo: 0.9% saline will be infused in an identical syringe over the same rate as if receiving a cell infusion, (See "Blinding of Placebo Infusion").

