5.1.8 Cross-Over and Follow-Up Visits

As part of the trial, the subjects will return to The University of Texas Health Science Center at Houston for 3 follow-up visits: 6 months (+/- 14 days), 1 year post-treatment (+/- 21 days), and 2 years post-treatment (+/- 21 days). Each visit will take place over 1-2 days in which the subject will undergo outpatient assessments that include physical and videotaped neurological exams, laboratory tests, chest radiograph, oxygen saturation monitoring, psychological testing, and quality of life measures. DTMRI will be performed at the 1 and 2 year post-treatment visits.

Prior to the 1 year follow-up visit, the treatment blind will be broken and the parent(s)/LAR notified. At this time, the parent(s) of children in the placebo group may choose to have their child admitted to the Children's Memorial Hermann Hospital pediatric unit for bone marrow harvest and infusion. All procedures will be followed in the same manner as was done for the Treatment Group.

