5.2.10 Cross-Over and Follow-Up Visits

As part of the trial, the subjects will return to The University of Texas Health Science Center at Houston for 3 follow-up visits: 6 months (+/- 14 days), 1 year post-treatment (+/- 21 days), and 2 years post-treatment (+/- 21 days). Each visit will take place over 1-2 days, and the subject will undergo outpatient assessments which include physical and videotaped neurological exams, laboratory tests, chest radiograph, oxygen

saturation monitoring, psychological testing, and quality of life measures. DTMRI will be performed at the 1 and 2 year post-treatment visits.

Prior to scheduling the 1 year follow-up visit, the treatment blind will be broken and the parent(s) notified. At this time, the parent(s) of children in the placebo group may choose to have their child admitted to the Children's Memorial Hermann Hospital Pediatric ICU/MICU for cord blood cell infusion. If the subject's parent(s) agrees to the cord blood infusion, the study coordinator will notify the Director of GSCL of the scheduled visit date. The Director will then request that the cord blood be shipped from CBR. The frozen cord blood unit will be shipped overnight to the GSCL 7 – 14 days prior to the scheduled procedure. The cord blood will be kept frozen until the morning of the infusion. All procedures will be followed in the same manner as was done for the Treatment Group.

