6.4.9 Secondary Imaging Outcome Measures & Correlation with Functional Outcome

As noted in the section, "CP Neuroimaging", cerebral palsy is a clinical diagnosis comprising a heterogeneous group of patients. This heterogeneity is manifest both in the dominant clinical symptom complex, but also in the imaging correlates of the symptoms. To that end, prior to treatment this study will quantify the degree of functional impairment (GFCMS level), and correlate it with the CP subtype and imaging abnormality. The imaging ROIs will be prospectively identified pre-treatment. Then, according to the qualitative and quantitative metrics, the imaging data will be recorded. Post-treatment, these same ROIs will be compared to the baseline data, and correlated with any changes in functional outcomes as measured by specific tasks on the GFCMS. Ultimately, the changes in WM and GM ROIs that are associated with CP will be compared with and without treatment using autologous bone marrow derived mononuclear cells or autologous cord blood mononuclear cells. These data will provide a structural metric around which future studies could be powered. Further, these data may provide potential mechanistic targets in terms of structural preservation and restoration in patients with CP.

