8. CRITERIA FOR INTERVENTION DISCONTINUATION

8.1 Description of Subject Completion

Subjects are considered to have completed the study if they have undergone the BMMNC/hUCB infusion at either the baseline or the 1 year cross-over visit and have completed the 2 year end of study visit.

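### The imaging Group-by-Time model runs to 2 years although sham children are offered cells at 1 year, so its 2-year, linear and trimmed Group terms do not estimate cells versus control

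*Combined protocol and SAP*

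**What the plan says.** Section 9.1.2 plans repeated measures ANOVA or ANCOVA for the imaging outcomes with "Group (Treatment, Control) as the between-subjects factor and Time of Assessment (baseline, 1 year, and 2 years"). It examines interactions, trims non-significant terms, and runs a trend analysis to choose between a linear and a quadratic function of time.

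Section 3 randomises 30 children 2:1 to treatment or sham. It states that at the 12-month visit "those subjects who originally received the sham will be offered the BMMNC or hUCB treatment". Crossover is optional: in section 5.1.8 "the parent(s) of children in the placebo group may choose to have their child admitted", and section 5.2.10 likewise leaves it to the parents. The blind is lifted first: "Prior to scheduling the 1 year follow-up visit, the treatment blind will be broken and the parent(s) notified". Section 8.1 counts a child as completing after having "undergone the BMMNC/hUCB infusion at either the baseline or the 1 year cross-over visit" and attending the 2-year visit.

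Objective 1.2 asks whether outcomes improve "compared with subjects in the control group". Section 6.4.9 adds: "Ultimately, the changes in WM and GM ROIs that are associated with CP will be compared with and without treatment", and says of the results: "These data will provide a structural metric around which future studies could be powered".

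Section 9 does not mention the crossover.

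**The concern.** A two-level Group factor carried through all three visits treats the control group as unexposed throughout. By design, that holds only up to the 1-year visit. After that, some or all controls have received cells, and the model has no term and the text no rule for it. If cells work, part of the planned output then measures the effect of timing, diluted by however many families accept the offer.

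What is at stake is the secondary efficacy estimate. Section 3 wants point estimates for a larger efficacy study and section 6.4.9 wants a structural metric for powering later work. An estimate that moves with parental uptake serves neither purpose well. Because the handling of about 10 controls is not written down, it could also be settled after the data are seen.

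**Working it through.** **Inputs from the documents.** N = 30 at 2:1 gives 20 treated and 10 sham (10 and 5 within each cell source). Imaging is at baseline, 1 year and 2 years. The significance level is 0.05, with no multiplicity adjustment (9.1.1). The plan gives no SD, visit correlation, uptake or power for imaging, so there is no power figure to reproduce.

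**Assumptions.** Constant effect d from 1 year after cells onward; uptake u from 0 to 1; SD 1 at each visit; equal correlation r between visits; no attrition. The illustration uses d = 0.5 and r = 0.8.

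**Step 1: mean profiles.** Treatment is (0, d, d). Control is (0, 0, ud). The difference at baseline, 1 and 2 years is (0, d, d(1-u)). At u = 0, 50, 80 and 100% the 2-year difference is d, 0.5d, 0.2d and 0.

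**Step 2: Group main effect if the interaction is trimmed.** It averages the three visits: [0 + d + d(1-u)]/3 = d(2-u)/3. That is 0.67d at u = 0 and 0.33d at u = 100%. With d = 0.5 SD it is 0.33 SD and 0.17 SD. The drop from 0.50 to 0.33 comes from averaging in baseline; only the drop from 0.33 to 0.17 comes from crossover.

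**Step 3: power of the named tests.** With 1/20 + 1/10 = 0.15:

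- Linear contrast (2 years minus baseline): SD = sqrt(2(1-r)) = 0.632. At u = 0 the non-centrality is 0.5/(0.632 x sqrt 0.15) = 2.04, or about 51% power. At u = 100% the contrast is zero.
- Quadratic contrast (1, -2, 1): SD = sqrt(6(1-r)) = 1.095. Its size is d at u = 0 (non-centrality 1.18) and 2d at u = 100% (2.36).
- Omnibus interaction: profiles (0, d, d) and (0, d, 0) have the same centred sum of squares, 2d²/3. The non-centrality is 2(0.25)/3/(0.15 x 0.2) = 5.56 at both ends.

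Simulation, with 0, 5, 8 or 10 of the 10 controls crossing over:

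| Uptake | Linear | Omnibus | Quadratic | 1-year ANCOVA |
|---|---|---|---|---|
| 0% | 51% | 53% | 21% | 53% |
| 50% | 15% | 39% | 39% | 53% |
| 80% | 6% | 44% | 53% | 53% |
| 100% | 5% | 53% | 62% | 53% |

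The 1-year ANCOVA averages 0.50 SD at every uptake. Over r = 0.7 to 0.9 its power is 40 to 80%; at full uptake the omnibus test has 37 to 83% and the quadratic 46 to 90%, with the linear test at 5% throughout.

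**Step 4: effect of trimming.** At full uptake the omnibus interaction is non-significant in 47% of trials at r = 0.8. If it is then dropped, what remains is the averaged Group term of step 2.

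**The case against.** Several points on the other side stand.

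- *Power is not lost overall.* Omnibus power is the same at full uptake as with no crossover, and quadratic power is higher.
- *The 2-year contrast is still randomised.* A reader might infer that the named tests cannot separate a lasting effect from one that has faded, because a lasting effect with full crossover and a faded effect with none share the profile (0, d, 0). Uptake will be known, however. At full uptake a lasting effect gives a 2-year difference of 0 and a faded one gives -d, and the linear test rejects in 5% against about 50% of trials. The contrast can be read as early versus delayed cells.
- *Group has a default reading.* A between-subjects factor does not change between visits, so it most naturally means as randomised.
- *The time origin is largely given.* A reader might infer from section 9.1.1, which times follow-up from cell treatment, that 2 years is undefined for controls. That sentence concerns the safety exploration. Section 3 calls the visit at which sham children are offered cells the 12-month post-treatment visit, which starts the clock at the first infusion, and Appendix A shows a single 2-year visit.
- *Some controls may be untreated at 2 years.* A reader might infer the opposite from section 8.1. That section defines completion, not the analysis set. Crossover is optional, and section 8.4 asks children who do not complete study treatment for the same data as those who withdraw.
- *Efficacy is secondary.* Section 9.2 calls this primarily a safety study.

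These points narrow the concern without removing it. A fixed Group factor, followed as written, still yields 2-year, linear and trimmed terms that answer a different question from objective 1.2, and the plan does not say so.

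**Conclusion.** The plan should be changed. The randomised comparison of cells with control ends at the 1-year scan, and section 9.1.2 does not recognise this. Under a constant effect the 2-year difference shrinks to d(1-u). The planned choice between a linear and a quadratic trend then depends on how many families accept crossover as well as on biology. The algebra needs only the constant-effect assumption; the power figures also rest on the assumed d, r and uptake. If the effect is e1 at 1 year and e2 at 2 years after cells, the 2-year difference is e2 - u x e1, which may be of either sign. The weakness is confined to estimating and interpreting a secondary objective.

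**What to change.** In 9.1.2:

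- Name baseline to 1 year as the randomised comparison that answers objective 1.2. Use ANCOVA of the 1-year value on baseline value and Group as randomised, with cell source and baseline age as between-subject covariates and intracranial volume for volumes. Keep Group whatever its p-value. (Age is now listed as a within-subjects factor, where it coincides with Time.)
- Keep the as-randomised 2-year contrast, labelled early versus delayed cells. Report uptake and decliners, and add a descriptive summary by time since cell infusion.
- Confirm that visits are counted from the first infusion, cell or sham.
- Use pre-crossover data for the Group term in the brain-behaviour models and in 6.4.9.

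Record whether each crossover-admission scan came before or after infusion. Appendix A puts both in one admission, and section 5.2.7, carried over by 5.2.10, allows either order for cord blood. Exclude post-infusion scans in a sensitivity analysis only: losing 5 of 10 control values would cut 1-year power from 53% to about 34% and widen the 95% half-width from 0.48 to 0.63 SD.

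**Cost.** Text changes and recorded times; no new visits. At full uptake the 1-year ANCOVA gains nothing over the omnibus test and has less power than the quadratic contrast (53% v 62%). Three uninformative covariates would lower it to about 49%. The 1-year visit follows unblinding, so attendance should be reported by group. As a hypothetical, if the 2 (or 4) of 20 treated children with the worst 1-year change stayed away, the estimate would shift by about 0.11 (0.20) SD at r = 0.8.

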9. STATISTICAL CONSIDERATIONS

9.1 Outcomes

9.1.1 Primary Safety Objective

Baseline characteristics of participants will be summarized using descriptive statistics and tabulations. Evaluation of data will be guided by exploratory analyses. All results will be reported as point estimates (percentages for binary outcomes and means \pm SD and median (range) for continuous outcomes) with corresponding interval estimates (two-sided 95% confidence intervals). No adjustments for multiple comparisons will be made and a p-value of 0.05 will be considered statistically significant.

These data are collected over time and will be longitudinal in nature with several predefined points of follow-up. We will use analytic strategies and methods applicable to such designs. For each participant in the cohort we have a set of "k" independent variables $\mathbf{x}' = (x_1, x_2, ..., x_k)$, of which some may be time varying (e.g., blood pressure) and others do not change over time (e.g., gender). In addition, the outcome variables of interest are also measured repeatedly over time (e.g., temperature, signs of infection, neurological exams, CBC, chem-20). We plan to explore any changes over time between hospital discharge and long-term follow-up at 6 months, 1 year, and 2 years after cell treatment with repeated measure model analyses. In this study, we plan to explore and identify potential factors associated with time to SAEs, AEs, death (refer to section 6.2), loss to follow-up (short term and long term), and improvements in functional outcomes (refer to section 6.3). We plan to explore the factors associated with the time to an event using survival analysis methods which incorporate information about the timing of withdrawals, deaths, and functional improvements (if any) of subjects during the follow up period. We plan to first use descriptive statistics to explore the characteristics of the subjects among events and then will use the Kaplan-Meier method to estimate the time to an event. Combined, these secondary analyses may provide useful preliminary estimates for the design of future cell studies.

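### The trimming rule for the imaging models in 9.1.2 would delete Group x Time, the term that carries the treatment effect, whenever it is non-significant

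*Combined protocol and SAP*

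**What the plan says.** Section 9.1.2 sets out a repeated-measures ANOVA or ANCOVA for the imaging outcomes. Group (Treatment, Control) is the between-subjects factor, with "Time of Assessment (baseline, 1 year, and 2 years) and Age as the within-subjects factors". The covariate named for this model is intracranial volume, for the macrostructure analyses; demographic variables may be added if the groups prove unlike. Baseline is thus a level of the outcome and not a covariate.

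The model-building rule is that the analysts "will examine the Age x Group x Time interaction and two-way interactions for each analysis and will trim non-significant terms from each model". The two-way interactions of Age, Group and Time are Age x Group, Age x Time and Group x Time. No term is exempted and no hierarchy rule is given.

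Section 6.4.9 states the aim. "Post-treatment, these same ROIs will be compared to the baseline data", and the changes are then compared with and without cell treatment. The same section wants the data as a metric for powering later studies.

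Section 9.1.1 says that "a p-value of 0.05 will be considered statistically significant", with no multiplicity adjustment, and promises point estimates with "two-sided 95% confidence intervals". It does not say for which contrast.

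**The concern.** Dropping a non-significant nuisance interaction, such as Age x Time, is ordinary practice. Dropping Group x Time is different, because in this model that term is the answer to the question in 6.4.9. A study of 30 children will often miss significance on a real effect of moderate size. In exactly those cases the rule takes the estimate out of the model, and the plan names nothing to report instead.

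The stake is the use of the imaging results as input to a later trial. An estimate that is kept or dropped according to its p-value is a poor basis for that.

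**Working it through.** **1. Inputs from the documents.** "A total of 30 subjects (15/arm) will be enrolled into the study" (section 3), randomized 2:1, so 20 cells v 10 sham when the two cell sources are pooled, or 10 v 5 within one source. Alpha is 0.05, and scans are at baseline, 1 year and 2 years. Sham subjects are offered cells at 12 months (sections 3, 5.1.8 and 5.2.10).

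**2. Inputs the documents do not give.** Section 3 cites a 15% effect on volumes but gives no SD, so it cannot be put on an SD scale. There is no visit correlation and no dropout rate. The plan has no figure of its own on this point to reproduce. I assume SD 1, equal correlation rho between visits (compound symmetry) and no dropout, ignore Age and intracranial volume, and vary rho and the effect d.

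**3. Where the treatment effect sits.** Let the true group differences be (0, d, d) at baseline, 1 year and 2 years if sham subjects stay untreated, or (0, d, 0) if all cross over and fully catch up by year 2. The change from baseline differs between groups only through Group x Time, or through Age x Group x Time if the effect varies with age.

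**4. How often Group x Time is trimmed.** The test is F on 2 and 2 x 28 = 56 df, with critical value 3.16. Its noncentrality is

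lambda = [20 x 10 / 30] x S / (1 - rho),

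where S is the sum of squared deviations of the three differences from their mean. For (0, d, d), S = (4/9 + 1/9 + 1/9)d^2 = (2/3)d^2. For (0, d, 0) it is also (2/3)d^2, so the trimming rate is the same in both cases. Example: d = 0.5 and rho = 0.8 give lambda = 6.667 x 0.1667 / 0.2 = 5.56, and the chance of F below 3.16 is 0.47.

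| True effect, 20 v 10 | rho 0.7 | rho 0.8 | rho 0.9 |
|---|---|---|---|
| 0.3 SD | 84% | 78% | 60% |
| 0.5 SD | 63% | 47% | 16% |
| 0.8 SD | 23% | 8% | 0.2% |

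Within one cell source (10 v 5), a 0.5 SD effect is trimmed in 81%, 73% and 50%. At rho 0.95, with 20 v 10 and 0.5 SD, it is trimmed in only 1%.

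**5. What remains after trimming.** If Group is non-significant too, the same wording can remove it, and no treatment term is left. Otherwise the Group main effect remains, and its expected value is the mean over the three visits:
- sham subjects stay untreated: (0 + d + d)/3 = 0.67d
- sham subjects fully catch up by year 2: (0 + d + 0)/3 = 0.33d

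These fractions do not depend on SD or rho. Simulation (20,000 trials, 20 v 10, d = 0.5, rho 0.8) agrees: among trimmed trials the main effect averages 0.33 SD, or 0.16 SD with catch-up.

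**6. Precision.** With sqrt(1/20 + 1/10) = 0.387:
- Group main effect: SE = sqrt((1 + 2rho)/3) x 0.387 = 0.346, 0.361, 0.374 at rho 0.7, 0.8, 0.9
- baseline-adjusted 1-year difference: SE = sqrt(1 - rho^2) x 0.387 = 0.277, 0.232, 0.169

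**7. Error rate if both terms are read as tests of treatment.** Under compound symmetry the two tests are close to independent. With no true effect, the chance that at least one reaches p < 0.05 is 1 - 0.95^2 = 9.75% per variable.

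**The case against.** A reader might infer that the trial will report the Group main effect as its treatment effect, and so publish a diluted estimate with nearly twice the nominal error rate. The documents do not support this. Section 9.1.2 never says how a leftover Group term will be read, and it may be trimmed as well. The interactions are examined before anything is dropped, so a Group x Time test at nominal 5% exists. If Age x Group x Time were kept, a hierarchical fit would keep Group x Time with it. The dilution in step 5 and the 9.75% in step 7 are therefore conditional.

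A reader might also fix on two thirds as the size of the dilution. That needs sham subjects to stay untreated to year 2, whereas the protocol offers them cells at 12 months.

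The trimming rates rest on assumed values, and with a large effect or very high scan-to-scan correlation the rule would rarely apply. That is correct, and it is why a range is shown.

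Finally, safety is the primary objective and 9.1.1 describes the evaluation as exploratory. This limits the severity. It does not remove the point, because 2.2 calls the imaging outcome the primary measure of efficacy and 6.4.9 wants it for powering later studies. The general promise of intervals in 9.1.1 does not help, since it sits under the safety heading and names no contrast.

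**Conclusion.** The rule is wrong as written and should be fixed. That part follows from the text alone: baseline is a level of Time, Group x Time is among the terms that may be trimmed, and no other contrast is named as the treatment effect. How often the rule would apply is not known from the documents. Under the assumptions in step 2 it ranges from 0.2% to 84% over effects of 0.3 to 0.8 SD and rho of 0.7 to 0.9, and is 47% at 0.5 SD and rho 0.8. If the leftover Group main effect were read as the treatment effect, it would target between one third and two thirds of d in the two cases considered. The primary safety analysis is not affected.

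**What to change.** In 9.1.2:
- Exempt Group x Time, and the Group term that it contains, from trimming.
- For every imaging variable, report the baseline-adjusted Group difference at 1 year with its 95% confidence interval, whatever its p-value. One year is the last scheduled visit before follow-up on cells can begin in the sham group.
- State that the Group main effect averaged over baseline is not a treatment effect.
- Report Age x Group x Time as exploratory.

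Exempting Group x Time cures the defect in itself. Naming the 1-year difference is an additional choice, which the 12-month crossover justifies. The cost is a few sentences and no new data. The downside is that wide, non-significant intervals will be reported openly, which suits a study of this size.
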